3.1.3 Exploratory Efficacy Objectives

The exploratory objectives of this study are:

- To evaluate the effect of high dose IVIG plus SMT versus SMT alone with regard to quantitative severe acute respiratory syndrome coronavirus 2 (SARS-CoV-2) viral load and anti-SARS-CoV-2 antibodies in hospitalized subjects with COVID-19.
- To evaluate whether high dose IVIG plus SMT versus SMT alone reduces the frequency of hyperinflammation based on a pre-specified biochemical definition through Day 29.
- To evaluate cytokine profile changes from baseline for high dose IVIG plus SMT versus SMT alone through Day 29.

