All subjects will be followed daily through Day 10. After Day 10, if subjects are discharged from the hospital, evaluations at Day 15 and 29 are required. Berlin criteria for ARDS ([Appendix 3](#)) and SOFA score ([Appendix 4](#)) will be assessed on Day 1, 5, 15, and 29. Subjects remaining hospitalized will be followed daily through Day 29. Days 15±1 and 29±1 may be performed at the study site or, if deemed appropriate, at an alternate site (e.g., subject's residence, local healthcare professional's site) under the care and supervision of trained healthcare personnel. If an in-person visit is unable to be conducted for Day 15 or

GRIFOLS Bioscience Industrial Group	Number	BLG-CL-PR7-000020	Version	4.0	Status	Effective	Effective Date	19-Jul-2021
	GC2007 - A Multicenter, Randomized, Open-label Parallel Group Pilot Study to Evaluate Safety and Efficacy of High Dose Intravenous Immune Globulin (IVIG) plus Standard Medical Treatment (SMT) versus SMT alone in						Page	34 of 91

Day 29, the study site will make a phone call to the subject to obtain as much information as possible remotely (e.g., Ordinal Scale, clinical features key symptoms, supplementation oxygen use, SAEs and TEAEs, concomitant medications). Phone Checks will occur at Day 60 and Day 90 for vital status (living or deceased), any hospital re-admissions or serious/non-serious adverse events after the Day 29 Final Clinic Visit. Details are provided in [Appendix 1](#) (Schedule of Study Procedures). Clinical status will be evaluated for all hospitalized subjects daily with vital signs, Ordinal Scale (7 categories analogous to Cao et al. 2020), and NEWS at Screening/Baseline and during IVIG plus SMT or SMT alone treatment and during Follow-up. The NEWS calculation is delineated in [Appendix 2](#) and can be calculated using the on-line web tool at <https://www.mdcalc.com/national-early-warning-score-news> .

For subjects in the combination arm (IVIG plus SMT) all laboratory samples must be drawn prior to infusion of IVIG, if laboratory assessments are required for a day in which IVIG is being infused.

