#### **4.2 Analysis Populations**

The following three analysis populations will be defined for this study:

The intent-to-treat (ITT) population is defined as all subjects who are randomized. All efficacy analyses will be carried out using the ITT population based on the randomized treatment.

The Per-Protocol (PP) population is defined as the subset of subjects included in the ITT population who do not present major protocol violations which might have an impact on the primary efficacy endpoint, and complete at least 80% of the IP. The primary efficacy analyses will be carried out using the PP population if different from the ITT population.

The Safety (SAF) population for the combination arm is defined as the subset of subjects who receive at least any amount of Gamunex-C in addition to SMT. The SAF population for the SMT alone arm will include all subjects randomized to this arm, because by definition SMT is universally provided and hence all randomized subjects would have received SMT. All safety analyses will be carried out using the SAF population based on the treatment actually received rather than randomized treatment.

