#### **4.4 Handling of Dropouts or Missing Data**

Missing data will be treated as missing and no method for imputation is planned for study population or safety analyses except for the partial end dates/times for concomitant medications (Section 5.6) and partial onset dates/times for AEs (Section 7.2.1). When applicable, missing data for binary and selected continuous efficacy endpoints will be imputed using a most conservative/worst case approach, and the related details are described in Section 6.

Time to event endpoints will have events coded as right censored or competing events per the

following table:

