**Table 1 Missing Data and Competing Events Coding for Time to Event Data Analyses**

Endpoint	Right Censoring and Competing Events
Subject Survival	Subjects who are still alive as of the last known follow-up will be right censored as of the date of last subject contact when the subject was known to be alive.
Time to actual ICU Discharge or Medical Equivalence of ICU Discharge (if different from actual ICU discharge date)	Subjects who did not discharge or medical equivalence of discharge from the ICU at any time during follow-up will be right censored as of the date of last subject contact when the subject was known to be in the ICU. Subject death will be considered a competing event. Competing risk methods e.g., cumulative incidence function (CIF) will be used to account for competing events in the analysis.
Time to actual Hospital Discharge or Medical Equivalence of Hospital Discharge (if different from actual hospital discharge date)	Subjects who did not discharge or medical equivalence of discharge from the hospital at any time during follow-up will be right censored as of the date of last subject contact when the subject was known to be in the hospital. Subject death will be considered a competing event. Competing risk methods e.g., cumulative incidence function (CIF) will be used to account for competing events in the analysis.
Time to Clinical Response	Subjects who did not experience clinical response or died at any time during follow-up will be right censored as of the date of last non-missing assessment of NEWS on or prior to Day 29.

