## **6.3 Exploratory Efficacy Endpoints and Analyses**

- Change from baseline in quantitative SARS-CoV-2 viral load by NAT or PCR (RT-PCR) to Days 5, 15, and 29 will be summarized for each treatment group by visit.
- Change from baseline in quantitative anti- SARS-CoV-2 IgM and IgG antibodies to Days 5, 15, and 29 will be summarized for each treatment group by visit.
- The proportion of subjects with evidence of hyperinflammation on Days 1, 5, 15, and 29 will be tabulated by treatment group. For this analysis, the denominator for calculating the

proportion at each visit and within each treatment group will be the number of subjects with non-missing values for Lymphocyte counts AND for at least 2 of the following 4 lab parameters: Ferritin, LDH, D-Dimers, and C-reactive protein (i.e., the number of subjects for whom evidence of hyperinflammation could be assessed).

- Change from baseline in cytokine profile (IL-1 $\beta$ , IL-10, IL-6, IL-8 IL-2, interferon  $\gamma$ , and TNF- $\alpha$ ) to Days 5, 15, and 29 will be summarized for each treatment group by visit.

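### The hyperinflammation proportions at Days 5, 15 and 29 cover only survivors with samples, so a mortality difference can bias the arm comparison and, under some assumptions, reverse it

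*SAP*

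**What the plan says.** The exploratory objective (Protocol 3.1.3, repeated in SAP 2.1.3) is to find out whether IVIG plus SMT "reduces the frequency of hyperinflammation based on a pre-specified biochemical definition through Day 29". The analysis in SAP 6.3 is a tabulation: "The proportion of subjects with evidence of hyperinflammation on Days 1, 5, 15, and 29 will be tabulated by treatment group". The denominator at each visit and in each arm "will be the number of subjects with non-missing values for Lymphocyte counts" and for at least two of the four markers, that is, ferritin, LDH, D-dimer and CRP. No test, confidence interval or effect estimate is specified, and SAP 6.3 has no rule for death.

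Three other provisions bear on this:

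- SAP 4.2: "All efficacy analyses will be carried out using the ITT population based on the randomized treatment".
- SAP 4.4: where applicable, "missing data for binary and selected continuous efficacy endpoints will be imputed using a most conservative/worst case approach", with the details left to Section 6. SAP 6.3 gives no such detail for this endpoint.
- Protocol 4.2 (with 7.2.5 and 7.2.7): if a Day 15 or Day 29 visit cannot be held in person, "the study site will make a phone call to the subject to obtain as much information as possible remotely". The items listed as examples include no laboratory test. The SAP states that it is based on Protocol version 3.0, and its schedule footnote on alternate sites does not mention the phone contact.

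Elsewhere the SAP does deal with death. For time to discharge, "Subject death will be considered a competing event" (Table 1). ICU, hospital, ventilation and oxygen days are filled to Day 29 after death under stated conditions (SAP 6.2). Death is category 1 of the ordinal scale.

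**The concern.** The objective compares randomised arms, but from Day 5 on the table compares people selected after randomisation: those alive and sampled. That selection may well be related to the outcome. Protocol 2.3.2 gives the aim as damping the inflammatory cascade so as to lower mortality. Protocol 2 reports that raised D-dimer on admission was associated with death, and D-dimer is one of the four markers in the definition. If inflamed subjects die more often, an arm that keeps more of them alive also keeps more of them in its numerator.

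Phone-only contacts act at the other end. They would tend to remove discharged, probably healthier survivors, which raises the proportion among those left. At stake is the reading of one table offered as evidence on mechanism.

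**Working it through.** The documents give no planning rate for mortality or hyperinflammation and no power calculation (Protocol 9.2, SAP 9), so there is no figure to reproduce. From the documents I take about 100 subjects, 1:1, hence about 50 per arm. The only comparative Day 29 mortality they give is 11.6% vs 8.0%, from a cited remdesivir trial in a broader hospitalised population (Protocol 2). Every other rate below is an assumption.

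**Set-up.** Let mC and mT be mortality by the visit on SMT and IVIG, with mT below mC and nobody dying on IVIG who would have lived on SMT. Let hC and hT be the hyperinflammation rates, on SMT and on IVIG, in those who survive on either arm. Let hS be the rate in those who survive only on IVIG. All survivors are sampled at first.

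- Planned SMT proportion = hC
- Planned IVIG proportion = [(1 − mC)·hT + (mC − mT)·hS] / (1 − mT)
- Hyperinflamed or dead, SMT = mC + (1 − mC)·hC
- Hyperinflamed or dead, IVIG = mT + (1 − mC)·hT + (mC − mT)·hS

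**Illustration, 50 per arm.** On SMT 20 die and 6 of 30 survivors are hyperinflamed. On IVIG 10 die and 11 of 40 survivors are hyperinflamed.

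- Planned: 6/30 = 20.0% vs 11/40 = 27.5%, so IVIG looks 7.5 points worse.
- Hyperinflamed or dead: (20 + 6)/50 = 52% vs (10 + 11)/50 = 42%, so IVIG is 10 points better.

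The 11 can be made up as 6 of 30 plus 5 of the 10 extra survivors (no effect in those who survive either way). It can also be 5 of 30 plus 6 of 10, in which case IVIG lowers the rate from 20.0% to 16.7% in those who survive either way and the planned table still shows it as worse.

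**Other assumed rates (SMT vs IVIG, %).**

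| Mortality | hC / hT | hS | Planned | Hyperinflamed or dead |
|---|---|---|---|---|
| 40 / 20 | 20 / 15 | 50 | 20.0 vs 23.8 | 52.0 vs 39.0 |
| 30 / 20 | 20 / 15 | 50 | 20.0 vs 19.4 | 44.0 vs 35.5 |
| 20 / 10 | 20 / 15 | 50 | 20.0 vs 18.9 | 36.0 vs 27.0 |
| 11.6 / 8.0 | 20 / 15 | 50 | 20.0 vs 16.4 | 29.3 vs 23.1 |
| 11.6 / 8.0 | 20 / 20 | 50 | 20.0 vs 21.2 | 29.3 vs 27.5 |
| 40 / 20 | 20 / 20 | 20 | 20.0 vs 20.0 | 52.0 vs 36.0 |
| 5 / 3 (Day 5-like) | 20 / 16.7 | 60 | 20.0 vs 17.6 | 24.0 vs 20.0 |

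**Break-even.** The planned difference is zero when hS = [hC·(1 − mT) − (1 − mC)·hT] / (mC − mT). For hC/hT of 20/15:

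- 40 vs 20: (0.16 − 0.09)/0.20 = 35%
- 30 vs 20: (0.16 − 0.105)/0.10 = 55%
- 20 vs 10: (0.18 − 0.12)/0.10 = 60%
- 11.6 vs 8.0: (0.184 − 0.1326)/0.036 = 143%, which is impossible, so no reversal can occur

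**Grid.** I crossed six mortality pairs (11.6/8, 20/10, 30/20, 40/20, 40/30, 50/30) with hC/hT of 20/20, 20/15 and 30/20 and hS of 20, 50 and 80. The planned and death-inclusive differences had opposite signs in 21 of 54 cases.

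**Unsampled survivors.** Return to the illustration and suppose 5 SMT and 15 IVIG survivors, none inflamed, are reached only by phone.

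- The planned table becomes 6/25 = 24% vs 11/25 = 44%.
- A composite over deaths plus sampled subjects gives 26/45 = 58% vs 21/35 = 60%. The direction is now wrong, because every death is kept and living subjects are lost.
- Over all randomised, counting the unsampled first as not inflamed and then as inflamed: SMT 26/50 to 31/50 (52% to 62%), IVIG 21/50 to 36/50 (42% to 72%). The range shows openly what is not known.

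**The case against.** The case on the other side is substantial.

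- *The table is exploratory, untested and open about its denominator.* True, and this limits the consequence.
- *Deaths are reported elsewhere.* Mortality is the primary endpoint, with Kaplan-Meier estimates at Days 15 and 29, and death is tabulated on the ordinal scale at both days. A careful reader could piece much of the picture together. The hyperinflammation table itself does not separate the dead from the living but unsampled.
- *The planned table is not wrong about how many living subjects are inflamed.* In the illustration, 11/50 = 22% of all randomised IVIG subjects are alive and hyperinflamed against 6/50 = 12% on SMT, the same direction as the planned 27.5% vs 20%. Only counting death changes the answer. This stands. The composite answers a different question and belongs beside the planned proportion.
- *SAP 4.4 may already cover it.* Its worst-case rule reaches binary efficacy endpoints, but it defers to Section 6, and SAP 6.3 sets an available-case denominator. The more specific text probably governs. The two sections still need reconciling.
- *Deaths also remove samples from the viral load, antibody and cytokine summaries.* True. The hyperinflammation objective is the one worded as a reduction in frequency, which is why the denominator matters most here.

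**Conclusion.** The point holds as a minor one. From Day 5 on, the proportions describe survivors with samples, SAP 6.3 has no rule that brings the others back, and the comparison can be biased. A reversal against a death-inclusive comparison requires three things: an appreciable mortality gap by that visit, extra survivors who are more often inflamed than the rest, and an effect among those who survive either way that is too small to outweigh this. If the extra survivors have the same rate as the others, the planned difference is undistorted. At 11.6% vs 8.0% mortality a 20% vs 15% effect cannot be reversed. With no effect at all and hS at 50%, the planned difference there is only 1.2 points in the wrong direction. Early at Day 5 a reversal is likewise unlikely, and Day 1 is unaffected.

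A reader might infer that the arm with more deaths will necessarily show less hyperinflammation, or that the table will have the wrong sign. The documents do not support that, because they give no rates from which any of the three conditions could be judged. A reader might also expect harm to appear as benefit. One can construct this: 15 SMT and 20 IVIG deaths, with 7/35 = 20% vs 2/30 = 6.7% hyperinflamed. But it takes all five excess deaths from the seven inflamed survivors, and hyperinflamed or dead is then 22/50 = 44% in both arms, so no opposite sign is being hidden.

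**What to change.** In SAP 6.3, for Days 5, 15 and 29 and by arm:

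1. Tabulate all randomised subjects as dead, alive and hyperinflamed, alive and not hyperinflamed, or alive and not assessed, with percentages of all randomised. Say where a subject of unknown vital status goes. The rule in SAP 6.1 that counts such a subject as dead is limited to the primary analysis.
2. Add a sensitivity row, *hyperinflamed or died by that day*, with all randomised subjects as denominator. Give it as a range, with unassessed living subjects counted first as not inflamed and then as inflamed.
3. Label the existing proportion *among survivors with samples*.
4. State whether the worst-case rule in SAP 4.4 applies to this endpoint.

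The cost is a few rows in one table, from data already collected, and nothing planned is removed. The composite mixes death with a biomarker, so it should stand beside the planned proportion and not replace it.

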Respiratory samples for quantitative measurement of SARS-CoV-2 viral load by NAT or PCR (real-time RT-PCR) will be obtained on Day 1, and subsequently on Day 5 ± 1 day, Day 15 ± 1 day and Day 29 ± 1 day (obtained via nasopharyngeal swab). The results of these samples are not necessary for continuing on study. Similarly, blood samples for quantitative measurement of IgM and IgG antibodies to SARS-CoV-2 via enzyme linked immunosorbent assay (ELISA), Indirect Fluorescent Antibody (IFA) or other assay methodology will be drawn at the same time points: Day 1, and subsequently on Day 5 ± 1 day, Day 15 ± 1 day, and Day 29 ± 1 day. The results of these samples are not necessary for continuing on study.

Ferritin, D-dimer, CRP and Basic chemistry analytes (creatinine, albumin, alanine aminotransferase [ALT], total bilirubin, lactate dehydrogenase [LDH]) will be assessed on Day 1 and on Day 5 ± 1 day, Day 15 ± 1 day, and Day 29 ± 1 day. Hematology (hemoglobin, hematocrit, platelet count, absolute lymphocyte count, leukocyte count with differential) will be assessed Day 5 ± 1 day, Day 15 ± 1 day, and Day 29 ± 1 day. Direct antiglobulin test (DAT) will be performed on Day 1, and on Day 5 ± 1 day, Day 15 ± 1 day, and Day 29 ± 1 day. All routine laboratory tests will be assessed locally at the hospital/site's laboratory. A cytokine panel will be performed at the same time points. Cytokine panel includes IL-1 β , IL-10, IL-6, IL-8, IL-2, interferon γ , and TNF- α . Note: serum samples must be stored at -70°C for later analysis at a reference laboratory.

This clinical trial will consist of the following phases:

- Screening/Baseline (Day 1) during which eligibility criteria are reviewed. Once all eligibility criteria are met and all pre-infusion assessments are completed, IVIG administration can begin for those subjects randomized to the combination plus SMT arm as expeditiously as feasible.
- SMT, Observations, and Follow-up (Days 2 to Day 29): SMT will be provided to all subjects with daily assessments while hospitalized and follow-up from Day 2 through Day 29 ± 1 day (inclusive).

GRIFOLS					
Number	BLG-CL-PRT-000020	Version	4.0	Status	Effective
GC2007 - A Multicenter, Randomized, Open-label Parallel Group Pilot Study to Evaluate Safety and Efficacy of High Dose Intravenous Immune Globulin (IVIG) plus Standard Medical Treatment (SMT) versus SMT alone in Bioscience Industrial Group					
				Page	19-Jul-2021
					35 of 91

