7.1.3 Exploratory Efficacy Variables

The exploratory efficacy variables include:

- Change from baseline in quantitative SARS-CoV-2 viral load by NAT or PCR (real-time RT-PCR) to Days 5, 15, and 29
- Change from baseline in quantitative anti-SARS-CoV-2 IgM and IgG antibodies to Days 5, 15, and 29
- Proportion of subjects with evidence of hyperinflammation on Day 1, Day 5, Day 15, and Day 29 defined as:
 - Lymphocyte counts <1000 cells/ μ L, AND
 - Two of the following 4 criteria:
 - Ferritin > 500 ng/mL,
 - LDH > 300 U/L,
 - D-Dimers > 1000 ng/mL (fibrinogen equivalent units [FEU]) or > 2 times upper normal limit,
 - C-reactive protein (CRP) > 70 mg/L
- Change from baseline in cytokine profile (IL-1 β , IL-10, IL-6, IL-8 IL-2, interferon γ , and tumor necrosis factor- α [TNF- α]) to Days 5, 15, and 29

GRIFOLS Bioscience Industrial Group	Number	BLG-CL-PRT-000020	Version	4.0	Status	Effective	Effective Date	19-Jul-2021
	GC2007 - A Multicenter, Randomized, Open-label Parallel Group Pilot Study to Evaluate Safety and Efficacy of High Dose Intravenous Immune Globulin (IVIG) plus Standard Medical Treatment (SMT) versus SMT alone in						Page	48 of 91

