- Record details of mechanical ventilation parameters (start/end date/time)
- Record oxygen saturation (specify on or off oxygen supplementation)
- Record daily 24-hour fluid balance (intake and output) while in hospital
- Record body weight for assessing fluid balance twice daily on Days 1 through 5 inclusive (at least 8 hours should separate the time from the first recorded weight)

GRIFOLS Bioscience Industrial Group	Number	BLG-CL-PRT-000020	Version	4.0	Status	Effective	Effective Date	19-Jul-2021	Page	51 of 91
	GC2007 - A Multicenter, Randomized, Open-label Parallel Group Pilot Study to Evaluate Safety and Efficacy of High Dose Intravenous Immune Globulin (IVIG) plus Standard Medical Treatment (SMT) versus SMT alone in									

- Record SAEs and TEAEs
- Record standard care concomitant medications

All laboratory tests and serum and plasma samples are required for all study subjects, regardless of treatment assignment. For subjects randomized to IVIG plus SMT all laboratory samples must be obtained prior to the Gamunex-C infusion on the designated day.

On Day 5 ± 1 day the following *additional* assessments will be performed:

- Assessment of ARDS (Berlin Criteria) ([Appendix 3](#))
- SOFA score ([Appendix 4](#))
- Respiratory sample for quantitative measurement of SARS-CoV-2 viral load by NAT or PCR (real-time RT-PCR) (obtained via nasopharyngeal swab)
- Sample for quantitative measurement of IgM and IgG antibodies to SARS-CoV-2 (store serum samples frozen at -70°C for later analysis at an external lab)
- Serum Chemistry (creatinine, albumin, ALT, total bilirubin, LDH)
- Ferritin (serum), D-dimer (plasma, sodium citrate tube), CRP (serum)
- Hematology: absolute lymphocyte count and standard hematology (hemoglobin, hematocrit, platelet count, leukocyte count with differential)
- DAT
- Cytokine panel (IL-1 β , IL-10, IL-6, IL-8, IL-2, interferon γ , and TNF- α). Note: serum samples must be stored at -70°C for later analysis at a reference laboratory.

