### **2.2.3 Exploratory Efficacy Endpoints**

Exploratory efficacy endpoints include:

- Change from baseline in quantitative SARS-CoV-2 viral load by nucleic acid amplification technology (NAT) or polymerase chain reaction (PCR; real-time reverse transcriptase [RT]-PCR) to Days 5, 15, and 29
- Change from baseline in quantitative anti- SARS-CoV-2 immunoglobulin M (IgM) and IgG antibodies to Days 5, 15, and 29
- Proportion of subjects with evidence of hyperinflammation on Day 1, Day 5, Day 15, and Day 29 defined as:
  - a) Lymphocyte counts  $<1000$  cells/ $\mu$ L, AND
  - b) Two of the following 4 criteria:
    - i) Ferritin  $> 500$  ng/mL,
    - ii) LDH  $> 300$  U/L,
    - iii) D-Dimers  $> 1000$  ng/mL (fibrinogen equivalent units [FEU]) or  $> 2$  times upper normal limit,
    - iv) C-reactive protein (CRP)  $> 70$  mg/L
- Change from baseline in cytokine profile (interleukin (IL)-1 $\beta$ , IL-10, IL-6, IL-8 IL-2, interferon  $\gamma$ , and tumor necrosis factor- $\alpha$  [TNF- $\alpha$ ]) to Days 5, 15, and 29

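### SAP 6.3 counts a subject as assessable for hyperinflammation on any two of four markers, although two markers can confirm the condition but cannot rule it out

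*SAP*

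**What the plan says.** SAP 2.2.3 and Protocol 4.1.3 and 7.1.3 define the endpoint in two parts that must both hold. The first is "Lymphocyte counts <1000 cells" per µL. The second is "Two of the following 4 criteria", the criteria being ferritin, LDH, D-dimer and CRP above stated thresholds.

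The analysis in SAP 6.3 is descriptive: "The proportion of subjects with evidence of hyperinflammation on Days 1, 5, 15, and 29 will be tabulated by treatment group". The denominator at each visit and in each arm is the subjects with "non-missing values for Lymphocyte counts AND for at least 2 of the following 4 lab parameters", and the SAP describes this as "the number of subjects for whom evidence of hyperinflammation could be assessed". No numerator rule is given for a subject with an incomplete panel.

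SAP 4.4 says that, where applicable, "missing data for binary and selected continuous efficacy endpoints will be imputed using a most conservative/worst case approach" and refers to Section 6 for the details. Section 6.3 gives none for this endpoint.

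**The concern.** A two-of-four rule is not symmetric in what it takes to decide it. Two raised markers settle a 'yes', but a 'no' on the marker part needs three markers at or below threshold. A denominator that asks for any two markers therefore admits low-lymphocyte subjects whose status cannot be known. It also excludes subjects whose status is known: a lymphocyte count of 1000 or more is a certain 'no' whatever the markers show, yet such a subject is dropped if fewer than two markers are present.

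The table serves a stated exploratory objective, whether IVIG reduces the frequency of hyperinflammation. If undetermined subjects are scored 'no', missing laboratory values read as absence of the condition. If panel completeness differed between arms, part of any difference in the table would come from that. Two programmers could also produce different tables, one following 6.3 literally and one applying the worst-case sentence in 4.4.

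**Working it through.** The documents give no expected rate, missingness or power for this endpoint, so there is no stated figure to reproduce.

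**Step 1: which patterns are determined.** For a subject with lymphocytes <1000:

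| Markers observed | Raised | Status |
|---|---|---|
| 2 | 0 or 1 | unknown |
| 2 | 2 | yes |
| 3 | 0 | no |
| 3 | 1 | unknown |
| 3 | 2 or 3 | yes |
| 4 | any | determined |

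Every unknown pattern meets the 6.3 denominator rule. None is in the numerator unless something is imputed. No pattern gives a false 'yes'. This step needs no assumption.

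**Step 2: size, by illustration.** These inputs are assumptions, not taken from the documents: half of subjects have lymphocytes <1000; each marker is raised with probability q = 0.6, independently; each marker is missing with probability m, independently of everything else; lymphocytes are never missing; undetermined subjects are scored 'no'.

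Chance of at least two raised markers:
- of four: 1 − (0.4⁴ + 4 × 0.6 × 0.4³) = 0.8208
- of three: 3 × 0.6² × 0.4 + 0.6³ = 0.648
- of two: 0.6² = 0.36

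Chance of an unknown pattern: 3 × 0.6 × 0.4² = 0.288 with three observed, and 1 − 0.36 = 0.64 with two.

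True proportion: 0.5 × 0.8208 = 41.0%.

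The chance of observing k markers is C(4,k)(1−m)^k m^(4−k). At m = 10% this is 0.6561, 0.2916 and 0.0486 for k = 4, 3, 2, which sum to 0.9963.
- SAP proportion: 0.5 × (0.6561 × 0.8208 + 0.2916 × 0.648 + 0.0486 × 0.36) / 0.9963 = 0.3725 / 0.9963 = 37.4%
- Undetermined share: 0.5 × (0.2916 × 0.288 + 0.0486 × 0.64) / 0.9963 = 0.0575 / 0.9963 = 5.8%

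| m | True | SAP rule (unknown = no) | Undetermined | Unknown = yes |
|---|---|---|---|---|
| 10% | 41.0% | 37.4% | 5.8% | 43.2% |
| 20% | 41.0% | 33.8% | 11.1% | 44.9% |
| 30% | 41.0% | 30.5% | 15.7% | 46.2% |

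With q at 0.3, 0.5 or 0.7 and the lymphopenic share at 0.5 or 0.7, the shift at m = 10% runs from −2.6 to −5.3 points. With m = 0 there is none.

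**Step 3: the opposite error.** Keep q = 0.6 and half lymphopenic. Suppose that 10% of lymphopenic subjects have three markers, 5% have two, and the rest have four. The numerator is 0.5 × (0.85 × 0.8208 + 0.10 × 0.648 + 0.05 × 0.36) = 0.3902. If no subject with lymphocytes of 1000 or more is dropped, the result is 39.0%. If 10% of them are dropped for having fewer than two markers, it is 0.3902 / 0.95 = 41.1%. If 20% are dropped, it is 0.3902 / 0.90 = 43.4%. The truth is 41.0%, so the net error can go either way when missingness depends on status.

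**Step 4: would a determined-only denominator cure it?** Under the Step 2 assumptions, restricting to determined subjects gives 39.6/37.4/34.3% at m = 10/20/30%, against 41.0%. Among lymphopenic subjects alone it gives 84.5/86.8/89.0%, against 82.1%, and leaves 12/24/37% of them out. It is closer overall than the SAP rule but still biased, because a 'yes' needs two markers and a 'no' needs three.

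**The case against.** A reader might infer that the SAP scores undetermined subjects as negative and so biases the endpoint downward. The documents do not support that as a flat statement, for two reasons. First, 6.3 fixes only a denominator. Leaving undetermined subjects out of the numerator is the natural reading, but it is inferred, and the worst-case sentence in 4.4, if applied here, would score them 'yes' and push the proportion up. Second, Step 3 shows that the dropped known negatives can cancel or reverse the shift. The downward direction is certain only when missingness is unrelated to status.

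A reader might also infer a false treatment difference. That requires panel completeness to differ by arm. The protocol requires the same laboratory tests in both arms (7.2.3 and Appendix 1), and nothing in the documents shows a difference.

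The independence assumption probably overstates partial panels. All four markers are scheduled at the same visits, and a Day 15 or Day 29 visit done by phone would probably lose the whole panel; such subjects leave the denominator and cause none of the shift in Step 2. Partial panels remain possible: D-dimer needs its own citrate tube, LDH is listed separately under chemistry, and "All routine laboratory tests will be assessed locally at the hospital/site's laboratory".

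Finally, this is one exploratory table with no test. That limits the importance of the point, but it does not make the description of the denominator correct.

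**Conclusion.** The denominator rule in SAP 6.3 does not identify the subjects whose status can be assessed. It includes some whose status is unknown and excludes some whose status is known. This follows from the definition alone.

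The size is conditional. Under the Step 2 assumptions, 6/11/16% of the denominator is undetermined and the reported proportion falls from 41.0% to 37.4/33.8/30.5% at 10/20/30% missingness per marker. That rests on three things: undetermined subjects being scored 'no', missingness being independent of status, and assumed frequencies that the documents do not give. A fixed downward bias, or a spurious difference between arms, is not established. The effect on the trial's conclusions is small.

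**What to change.** In SAP 6.3, classify each subject at each visit as:
- positive: lymphocytes <1000 and at least two markers above threshold;
- negative: lymphocytes of 1000 or more, or at least three markers not above threshold;
- undetermined: anything else.

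Report the undetermined count by arm and visit. Give the proportion twice, with undetermined subjects counted all as 'no' and all as 'yes'. A single determined-only proportion should not replace these bounds, since Step 4 shows that it is biased too. State whether subjects with no sample at a visit enter the undetermined row or are listed separately, and say whether the worst-case sentence in SAP 4.4 applies to this endpoint.

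The cost is a derivation change in one exploratory table, with no new data. The downside is a visible undetermined row, which could be sizeable if partial panels are common, and a range in place of a single percentage.
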